Study interviews will either be directly administered by [name] or by research staff trained by [name]. [name] is a licensed clinical psychologist with extensive training and experience in the administration of structured and semi-structured diagnostic interviews in both research and clinical settings. [name] has previous experience administering the Structured Clinical Interview for DSM-IV (which requires similar knowledge and skills to administer as the M.I.N.I. 7.0.2), Addiction Severity Index, and Timeline Follow-Back procedure. In addition, instructions for the Positive-Neutral Future Events Interview were developed by [name] based on experience soliciting similar information through unscripted interviews during her pilot project (Pro1787). A series of qualitative interview questions were also developed by [name] based on her experiences working with Veterans in Contingency Management in both clinical and research contexts.

View: 3.4 Use of Medical Devices

Medical Devices

1.0

* Specify all devices used on this study:

Device Name Manufacturer Use of Device IDE Number(if Applicable) Device Brochure Description of Use
Risk Level Determined by Sponsor

acti32Champ EEG Acquisition System Brain Products GmbH Investigational Device Not Yet Approved for use actiChamp Manual(0.01) This is a nonmedical device that will be used for the acquisition of electroencephalography (EEG) data in accordance with manufacturer operating standards. This device is non-invasive and will only be used to monitor naturally-occurring biological signals and processes in vivo. The actiChamp is intended to be used for research applications only and is not sold, designed or intended to be used as medical devices as defined in EU Directive 93/42/EEC, nor is it intended to be used for other medical applications such as diagnosis or treatment of disease. The actiChamp hardware has been tested and certified as per the relevant EMC and electrical safety standards. A non-medical CE certificate is available on request. This equipment was reviewed and approved for purchase by the VAPHS Bio Medical Review committee on 5/9/2019. Non-Significant Risk

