View PRMQ(0.01) 0.01
View SLUMS(0.01) 0.01
View SOCRATES(0.01) 0.01
View SPSRQ(0.01) 0.01
View SSS(0.01) 0.01
View TRQ(0.01) 0.01

View: 4.1 Research study methods: analysis Plan

1.0 * Please describe the analysis plan for the study (it is acceptable to refer to the sponsor/multi-site protocol for section if applicable):

Data Analytic Plan.

EEG Data Preprocessing. Data from both incentive delay and flankers tasks will be visually inspected and band-pass filtered using parameters specific to each analysis. Data will subsequently be corrected for ocular, movement, and (if applicable) line noise artifact, using independent components analysis or possibly other methods. If necessary, bad channels will be replaced with interpolated data. Data from each task will be segmented into event-locked epochs. Epochs with significant residual artifact will be rejected and a current source density transformation may be applied to improve spatial resolution, prior to analysis, if deemed necessary. Alpha suppression will be computed for the pre-feedback reward anticipation interval in the Incentive Delay task by computing event-related spectral power in the alpha band (8-12 Hz), relative to a pre-response baseline interval. Differential alpha suppression to high magnitude tangible versus voucher prizes will be quantified at occipital sites (O1, Oz, O2) within the 1500 ms time window preceding feedback. For the Flankers task, ERN and conflict N2 amplitudes will be determined as follows. For response-locked event-related potentials, the negative peak amplitude of the difference wave computed for error vs. correct responses at sites FCz and/or Cz will be used as the measure of ERN amplitude. The sum of differences in stimulus-locked N2 amplitude between congruent vs. intermediate incongruity conditions and congruent vs. high incongruity conditions will be used to quantify parametric modulation of conflict N2 by differential control demands. For functional connectivity analyses, data will be bandpass filtered into targeted frequency bands (e.g., delta, theta, alpha, beta, and gamma). Theta frequency synchronization between ACC electrode sites (e.g., Cz, FCz) and IPFC electrode sites (e.g., F3, F4, F5, F6) will specifically be evaluated for error vs. correct and congruent vs. incongruent trials using synchronization likelihood or a similar approach. Exploratory

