Power Analysis and Sample Size. In analyses of baseline predictors of treatment response in CM recipients (estimated $n = 119$ -140) and long-term (i.e., six month) outcomes (estimated $n = 105$ -140), using the statistical rule of thumb of needing 10 observation per predictor, our originally projected sample size would provide adequate power to include 10-14 variables in regression-based analyses. Random Forest methods are further supported for an expanded set of variables, as this highly flexible and powerful approach has been validated in “wide datasets,” wherein the number of predictors exceeds the number of observations. With the anticipated enrollment of 140 participants, there will additionally be adequate power ($\beta = 0.20$, alpha = 0.05) to detect an effect size of $f = 0.12$ for the treatment adherence (adherent, non-adherent) X time (baseline, follow-up) interaction, supporting planned comparison of treatment-related change in neural and cognitive-behavioral measures between PBCM adherent and non-adherent Veterans. Assuming 15% attrition, the estimate of the detectable effect size for the treatment X time interaction for a total sample size of 119 is $f = 0.13$. The anticipated effect size of treatment-related change in synchronization likelihood between ACC-IPFC electrode sites is not known. However, previous work has established a medium-to-large effect size for treatment-related change in the ERN and N2 (in association with cognitive training).[74,75]

It was necessary to revise our original analytic plan to accommodate a smaller sample size than that originally projected. Recruitment under the current protocol was initially delayed due to institutional barriers that prevented timely acquisition of our EEG system. While recruitment was promptly initiated after our equipment was finally received, approximately three months later, all research activities were suspended due to risks posed by the COVID-19 pandemic. Due to the collection of EEG data and the nature of the interventions under study (e.g., need to be in the physical presence of the prize cabinet to potentially benefit from the increased psychological proximity of reward), it was not possible to convert the current protocol to be conducted fully remotely during the pandemic. A series of administrative

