Additional exploratory analyses may also be conducted to investigate trajectories of recovery during PBCM in relation to neuroadaptive change. I will receive specialized training in multilevel modeling approaches to longitudinal data analysis, including use of growth mixture models to resolve latent subgroups exhibiting distinct patterns of longitudinal change. For participants assigned to both PBCM conditions, longest duration of cocaine abstinence may be computed on a weekly basis from within-treatment urinalysis results and attendance (unexcused, missed appointments will also be considered to end a period of abstinence). Growth mixture modeling may subsequently be employed to evaluate intra-individual change in the longest duration of abstinence achieved during PBCM treatment and determine if distinct change profiles meaningfully represent inter-individual variance. If identified, subgroups exhibiting distinct trajectories in PBCM may also exhibit different patterns of neural recovery within functional connectivity networks underlying cognitive control and reward representation. Exploratory, network-based analyses may therefore also be conducted (if applicable) and may generate new insights into neuroadaptive processes that reflect and may also support sustained abstinence in CM. Cocaine users have previously been demonstrated to exhibit reduced interhemispheric functional connectivity within the dorsal frontoparietal control network, which is thought to support goal-directed top-down control of attention and behavior, as well as representation and anticipation of future rewards. My training in functional connectivity analysis of EEG data will support exploratory analysis of network-level disturbances in CUD, as well as potential treatment-related change in interhemispheric functional connectivity within the dorsal frontoparietal control network in relation to CM. Using methods previously described by my consultants, Drs. [name], [name], and [name], I may also employ synchronization likelihood to identify localized functional connectivity networks that significantly differ between CUD subgroups exhibiting different patterns of cocaine abstinence during CM. Briefly, pairwise synchronization likelihood will be computed between all pairs of EEG channels for reward- and control-

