related epochs derived from Incentive Delay and Flankers tasks, respectively. Non-parametric, network-based statistics will subsequently be employed to identify pairings which differ significantly between CUD subgroups at baseline and follow-up, including potential differences in interhemispheric functional connectivity within the dorsal frontoparietal control network. Training offered by my consultants would also afford the opportunity to combine synchronization likelihood with graph theoretic approaches to functional connectivity analysis. Consequently, additional exploratory analyses can target differences in network-level properties within local (e.g., strength, local efficiency, betweenness centrality) and global (e.g., path length, small worldness, global efficiency) functional connectivity structures. However, it is noted that additional exploratory analyses can only be undertaken if the final sample size is sufficient to support them.

Missing Data Strategies: Individuals lost to follow-up will be excluded from these analyses due to necessary inclusion of longitudinal measures from the follow-up timepoint. It is anticipated that covariates of interest will be available for all individuals who complete the follow-up assessment session. Specifically, treatment engagement will be determined on the basis of chart review and self-reported substance use will be evaluated on a weekly basis. For participants who miss one or more check-in assessment during the treatment period, the timeline follow-back procedure will be extended to evaluate the full period between the present and previous study contact. In my previous longitudinal study of substance users, I was able to collect all necessary follow-up data on 80.8% of my originally enrolled sample. However, it is also possible that unexpected circumstances may require imputation of missing data values. In such cases imputation of missing values will leverage available within- and between-subjects data.

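### Network-based statistics control error for a connected component, so they cannot identify individual pairings as significant, and the named interhemispheric difference needs its own test

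*Combined protocol and SAP*

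**What the plan says.** The exploratory analyses at the end of Specific Aim 2 (section 4.1, analysis plan) propose a whole-scalp connectivity comparison between patient subgroups with different abstinence patterns. The opening sentence sets the aim as using "synchronization likelihood to identify localized functional connectivity networks that significantly differ between CUD subgroups". Next, "pairwise synchronization likelihood will be computed between all pairs of EEG channels", for epochs from both EEG tasks. The test is then described: "Non-parametric, network-based statistics will subsequently be employed to identify pairings which differ significantly between CUD subgroups at baseline and follow-up". The same sentence singles out one effect of interest, a difference between subgroups in left-right connectivity of the frontoparietal control network.

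The plan gives no pair threshold, number of permutations, component measure or pair-level correction, and it lists no left-right pairs. It words the analysis as optional and allows it only if enough participants are available.

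**The concern.** The two sentences name different units of inference: the first a network, the second a pairing. Network-based statistics, in the usual sense, threshold every channel pair, join the pairs above threshold that share an electrode, and compare the size of each joined component with a permutation distribution of the largest component. A significant result says that the component is larger than chance would produce. It does not say which pairs inside it truly differ, because chance pairs that touch a true component are carried in with it.

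Interhemispheric connectivity is the one effect singled out, yet its detection depends on its layout. Left-right pairs that share no electrode do not join into a component. The plan does not say which layout is expected and gives no dedicated test.

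Two errors could follow. A list of significant electrode pairs could be carried into later work, such as the neurofeedback or brain stimulation research that the background anticipates. A true interhemispheric difference could also be reported as absent.

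**Working it through.** **Figures to reproduce.** The plan states no sample size, power, alpha or threshold for the network analysis, so there is nothing to reproduce. The neighbouring Aim 2 repeated-measures figures do reproduce. With noncentrality f²·N·2/(1−ρ) and ρ=0.5, the detectable f is 0.119 at N=140 (stated 0.12) and 0.130 at N=119 (stated 0.13).

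**Inputs.**
- Channels: not stated. 32 is assumed from the device name "acti32Champ EEG Acquisition System" in section 3.4, giving 32×31/2 = 496 pairs.
- Sample: the revised plan expects 36 participants with pre- and post-treatment data. A split of 18/18 is assumed.
- Also assumed: two-sided t-test per pair at 0.05, 0.01 or 0.001; components scored by edge count; component test at 5%; true differences of d=0.8 to 1.6 per pair.

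**1. Whole-graph error.** In simulation under the complete null (200 runs, 200 permutations each), any component was declared in 2.5%, 3.5% and 4.5% of runs at thresholds 0.05, 0.01 and 0.001. The method does what it promises for the graph as a whole.

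**2. Null pairs inside a true component.** Suppose all 16 pairs between 4 left and 4 right sites truly differ. Pairs touching at least one of these 8 electrodes number 496 − 24×23/2 = 496 − 276 = 220, so 220 − 16 = 204 null pairs would attach if they crossed the threshold. The expected number attaching directly is 204α. Each true pair has noncentrality d×√(18×18/36) = 3d on 34 degrees of freedom. Null share = null/(null + true).

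| Threshold | Null pairs, 204α | True pairs, 16×power (d=0.8; 1.2) | Null share by hand | Null share simulated |
|---|---|---|---|---|
| 0.05 | 10.2 | 16×0.645=10.3; 16×0.938=15.0 | 50%; 40% | 72%; 64% |
| 0.01 | 2.04 | 16×0.385=6.2; 16×0.801=12.8 | 25%; 14% | 27%; 17% |
| 0.001 | 0.20 | 16×0.141=2.3; 16×0.510=8.2 | 8%; 2% | 7%; 3% |

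The hand count omits null pairs that attach through other null pairs, which is why the simulated share is larger at 0.05. With independent errors at 0.01, the chance that at least one null pair attaches is 1 − 0.99^204 = 87%. Across simulations at 0.01 with other error correlations and true sets, 60-95% of significant results contained a null pair, and 14-52% of listed pairs were null.

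**3. Mirror-image pairs.** A pair sharing no electrode with another true pair is a one-edge component unless a chance pair attaches. With independent errors under the null, at least one such edge appears with probability 1 − 0.99^496 = 99% at 0.01, or 1 − 0.999^496 = 39% at 0.001. Alone, it cannot reach 5% by edge count. For four mirror-image pairs, simulation found at least one true pair in 3-6% of runs at d=0.8, 9-14% at d=1.2 and 13-16% at d=1.6.

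**4. A wider interhemispheric block.** The 16-pair block at d=0.8 was detected in 34%, 67% and 56% of runs at 0.05, 0.01 and 0.001 under one error structure. Across the error structures tried, detection ran from about 6% to about 80%. A max-statistic permutation over all 496 pairs found at least one true pair in 45-56%.

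**5. One averaged score.** Averaging k pairs with correlation r between them gives d/√[(1+(k−1)r)/k]. For k=4 and d=0.8:
- r=0.5: 0.8/√0.625 = 1.01, noncentrality 3.04, power 84%.
- r=0: 0.8/√0.25 = 1.6, noncentrality 4.8, power above 99%.

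The max-statistic approach found at least one of the same four pairs in 12-21% of runs.

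**The case against.** **The unit is already stated.** The introducing sentence speaks of networks, and what follows is offered as a summary, so pairings may be loose wording. That is a fair reading, but the sentence that says what will be called significant names pairings. An analyst who follows it would report pairs.

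**The method is inferred.** The plan does not define the statistics and points to consultants' methods that the document does not reproduce. This stands as a limit: the point applies to the standard component-permutation form. The scoring measure matters too. With components scored by summed excess t, four mirror-image pairs at d=1.2 were detected in 32-74% of runs, against 10-12% by edge count in the same check. At d=0.8 detection stayed at 6-18%.

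**Stronger readings.** A reader might infer that the analysis has no error control, or that an interhemispheric difference is almost undetectable. Neither is supported. Whole-graph error is held near 5%. The plan nowhere says the effect is confined to pairs sharing no electrode, and a difference across several left and right sites can form a component that is found as often as, or more often than, by a pair-wise method.

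**The averaged score is a favourable comparator.** Its power assumes that the right pairs were listed in advance. The low max-statistic figures show that part of the difficulty is 496 pairs at N=36 rather than the choice of method. Both remarks stand.

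**It is exploratory.** Subgroups must first emerge, the sample must suffice, and Hypothesis 2a rests on a separate repeated-measures analysis of prespecified theta synchrony. This limits the severity.

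**Conclusion.** The point holds for pair-level claims. As written, the plan would call individual pairings significant on the strength of a test that protects only the component. The size of the error depends on a threshold the plan does not give: about 15-50% of listed pairs null at 0.01, 64-72% at 0.05 and 3-7% at 0.001. The last two ranges come from one error structure and the 16-pair block.

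Detection of the interhemispheric difference is poor, roughly 3-16%, only for a few mirror-image pairs scored by edge count. For a wider block at d=0.8 it is anywhere from about 6% to 80%.

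All these figures rest on the assumed 32 channels, 18/18 split, effect sizes and error correlations, with Monte Carlo error up to about 3.5 points in the 200-run simulations. Severity is low: no primary conclusion depends on this analysis.

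**What to change.** Replace the sentence on network-based statistics in section 4.1 with wording such as:

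> Network-based statistics support a claim only about the component as a whole; pairs inside a significant component are described and not called significant. Any claim about a single pair uses a max-statistic permutation threshold over all pairs. Interhemispheric frontoparietal connectivity is tested separately, as one averaged score over left-right pairs listed in advance, by one permutation test.

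State the pair threshold, number of permutations and component measure alongside it, since the results above turn on them.

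The cost is wording and one extra test on data already collected. In simulation the max-statistic threshold gave 3.0-5.5% false positives under the complete null. The downside is that fewer single pairs can be claimed, and the averaged score has good power only if the listed pairs are well chosen.

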Weekly Check-In Appointments (12 Weeks). Participant outcomes (outpatient treatment engagement, % cocaine-negative urines, self-reported days of use) will be followed throughout the 12 week treatment interval; during this period the timeline follow-back procedure will be administered by phone or in-person on an approximately weekly basis. During the treatment interval, the timeline follow-back procedure will always be administered such that the beginning of the assessment interview corresponds with the last occurrence of the timeline follow-back procedure. In this way we will endeavor to collect self-reported substance use data for the full 12 week treatment interval. This effectively means that one or more missed check-in appointments may be administered at the time of the next check-in attended, if needed. Outpatient substance use treatment engagement and urinalysis results will be monitored through review of participant medical records. Participants will additionally be asked to provide regular updates regarding any changes in their housing status or medications (including changes in dosing schedule and/or clinic privileges for patients in medication-assisted treatment) and participation in non-VA substance use treatment (e.g., 12-step meetings in the community). For CM participants, this information may be gathered, in part or in full, during 1:1 CM treatment appointments. This information will, however, also be assessed during check-in appointments to ensure that relevant information is reliably tracked for all participants, regardless of current participation in CM sessions (see Supplemental Check-in Questions uploaded under Section 3.2).

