
Risks and Benefits: With respect to Substudy 1, participants will have the opportunity to receive a telemedicine version of CM that is not otherwise available at our site and this may benefit Veterans for whom remote treatment options are indicated or preferred. There are no significant risks associated with the proposed telehealth-based protocol - rather, it is expected that this CM option may be lower risk for some Veterans. This substudy will combine the use of an approved "standard of care" treatment option with approved VA telehealth technology (e.g., VVC) and so does not significantly deviate from standard clinical practice. However, due to the use of Veteran-administered oral fluid testing, this treatment protocol would currently only be permissible in the context of research. Participants will be informed of confidentiality and privacy considerations that are unique to telehealth at the start of each session (for example, ensuring that the Veteran has sufficient privacy in their current environment), as is typical of all such clinical interactions.

SUB-STUDY 2: REMOTE PHYSIOLOGICAL MONITORING FOR STATE-DEPENDENT PREDICTORS OF CRAVING AND USE

SUB-STUDY 2 Specific Aim: Establish feasibility of data collection using wearable sensors and identify promising physiological markers of stimulant craving and/or use between treatment encounters.

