Data Analytic Plan. The number of participants declining to participate in the sub-study, as well as feedback regarding acceptability of wearable device monitoring will be quantitatively and qualitatively summarized. Data collected through ActiGraph/Polar wearable devices will be reviewed, preprocessed, and analyzed using ActiLife software. The proportion of data rejected due to noncompliance (detected using ActiLife's Wear Time Validation Tool) or poor electrocardiography (ECG) signal quality (determined through visual inspection) will subsequently be computed. Valid data segments will be subject to additional analyses investigating potential markers of high-risk states in wearable data streams. Based on previous work and known cardiovascular effects of stimulants, periods of elevated resting heart rate

are expected to predict self-reported stimulant use and subsequent stimulant-positive urinalysis. For example, periods of elevated heart rate associated with cocaine craving can be distinguished from use events based on duration (30-40 minutes for craving versus 2 hours for use). The number and duration of elevated resting heart rate intervals will be investigated as potential predictors of self-reported and objectively verified stimulant use using a mixed effects logistic regression approach. Additional exploratory features extracted from ECG and activity data (e.g., heart rate variability (linked to craving in alcohol users), sleep efficiency (known to be impaired during early cocaine abstinence), and number/duration of physical activity bouts) may also be considered. These preliminary analyses will serve to identify promising state-dependent markers from wearable data streams for future investigation. Importantly, a mobile interface to be developed under a separate protocol (Pro3566) will support ecological momentary assessment of craving, stress, and substance use and these data will critically inform future efforts to distinguish physiological markers associated with high-risk for use – of relevance to delivery of in the moment interventions – from actual use events.

View: 6 Study Population Summary

Study Population Summary

1.0 * What is the maximum number of subjects you plan to enroll at VAPHS?

215 (Target Sample Size Primary Study = 140; an additional 1-5 Veterans may be invited to participate in Sub-Study 1)

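### Sub-Study 2 does not separate heart-rate intervals that precede stimulant use from intervals caused by it, so a same-window association can be reported as a predictor

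*Combined protocol and SAP*

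**What the plan says.** All references are to Section 5.1 (Sub-Studies, Sub-Study 2) unless another section is named.

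- **Purpose.** The title is "REMOTE PHYSIOLOGICAL MONITORING FOR STATE-DEPENDENT PREDICTORS OF CRAVING AND USE". The Specific Aim is feasibility of wearable data collection and to "identify promising physiological markers of stimulant craving and/or use between treatment encounters". The Data Analytic Plan adds: "Valid data segments will be subject to additional analyses investigating potential markers of high-risk states in wearable data streams".
- **Rationale.** The expected association is introduced by "Based on previous work and known cardiovascular effects of stimulants, periods of elevated resting heart rate" and completed by "are expected to predict self-reported stimulant use and subsequent stimulant-positive urinalysis".
- **Model.** "The number and duration of elevated resting heart rate intervals will be investigated as potential predictors of self-reported and objectively verified stimulant use", fitted "using a mixed effects logistic regression approach".
- **Duration contrast.** As an example, the plan says craving and use episodes can be told apart by length: 30–40 minutes for craving, 2 hours for use.
- **Status.** The analyses are called preliminary. Distinguishing high-risk markers from actual use events is left to future work with momentary assessment under a separate protocol.
- **Timing of the use data.** Section 4 (Weekly Check-In Appointments) says of self-report: "during this period the timeline follow-back procedure will be administered by phone or in-person on an approximately weekly basis". Section 3.5 gives twice-weekly urinalysis. The timeline follow-back description in Section 4 lists type, frequency and quantity of use, with no clock time.

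**The concern.** A marker of a high-risk state has to come before use. The plan's reason for expecting an association is a consequence of use. If intervals are counted over a day or a between-test window that contains the use event, the elevation caused by that event is part of the predictor. A positive coefficient then fits two readings: a state that precedes use, or the drug's effect on heart rate. The model as written cannot tell them apart.

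At stake is the label. The sub-study is meant to pick out markers for later investigation, and the plan links that later work to real-time intervention. A drug effect carried forward as a risk marker would point that work at the wrong signal.

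**Working it through.** **1. Is any time order set between heart rate and use?**

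| Element of the plan | What it orders |
|---|---|
| Model sentence | Nothing: no lag, window, unit of analysis or exclusion |
| The word *subsequent* in the rationale | Heart rate before the urine test, not before the use |
| Duration contrast | Nothing in the model: given as an example, with no classification or exclusion step |
| Deferral to momentary assessment | Future work only |

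**2. How wide are the windows?** Urinalysis twice weekly gives one result per 7/2 = 3.5 days on average, and at most 4 per participant in two weeks. Any use that turns a test positive, if it falls in that window, puts its own elevation of about 2 hours into the predictor. Self-report is at best daily, so on a use day the same thing happens.

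**3. Does including duration solve it?** Not as written. By the plan's figures one use event lasts as long as 120/40 = 3 to 120/30 = 4 craving episodes. If duration is summed (the plan does not say), it gives more weight to the intervals that the plan attributes to use.

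**4. Illustration.** The documents give no alpha, power, event rate or effect size for this sub-study, so there is no figure to reproduce. A simulation shows the mechanism.

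- *From the documents:* 45 participants (the ceiling on invitations), 14 days, so 45 × 14 = 630 person-days at most.
- *Assumed:* daily use probability 5%, 10%, 20% or 30% for a typical participant; between-participant SD 1.0 on the logit scale; 0.2 background long and 0.5 short intervals per day; use produces one long interval with probability 0.5 or 0.9; heart rate unchanged before use; test at 0.05.
- *Model:* logistic GEE clustered by participant, interval counts centred within person with the person mean as a second term, as a stand-in for the planned mixed model; 200 runs per setting.

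| Predictor of use on a day | Median odds ratio per interval | p < 0.05 |
|---|---|---|
| Same-day count, short and long pooled | 1.65–2.75 | 94–100% |
| Previous-day count, pooled | 0.91–0.97 | 5–13% |
| Same-day short intervals only | 0.97–1.01 | 4–8% |
| Same-day long intervals only | 3.70–19.65 | 100% |

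Ranges are over the eight settings. With 200 runs, the Monte Carlo standard error at 5% is √(0.05 × 0.95/200) = 1.5 percentage points. The 13% in the lagged row exceeds that noise. Part of the reason is the centring: the person mean over 13 predictor days includes the outcome day's own count for all but the last outcome day, which adds a covariance of −cov(count, use)/13. The odds ratios accordingly lie below 1, the opposite direction from a precursor.

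A second simulation used other assumptions: about 19% use days, use persisting from day to day, about one background interval per day, and 0.5, 1 or 2 extra intervals on use days. Same-day counts were significant in 97%, 100% and 100% of runs. Counts from a preceding use-free day were significant in 6–8%. The restriction to use-free days matters when use persists, because otherwise yesterday's drug effect predicts today's use. It kept about 62 of 119 use days (52%).

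**The case against.** The case on the other side is substantial.

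- **Detection is within the aim.** The aim names markers of craving and/or use. An association produced by use answers part of it. This stands: the fault is only in calling it a predictor or high-risk-state marker.
- **The plan recognises the problem.** It gives the duration contrast, calls the work preliminary and defers the separation. This stands, and a reader should not infer that the issue was overlooked. But nothing in the plan labels a same-window result as detection in the meantime.
- **The simulated 94–100% is not a false-positive rate.** A reader might infer that the sub-study would nearly always give a false positive. The documents do not support that. The plan's own hypothesis is that stimulants raise heart rate, and in the simulation that is true, so the figure is power to detect the drug effect. The rates are assumed, and the pooled counts leave duration out.
- **Short intervals behaved well.** Modelled alone, they were significant in 4–8% of runs. This supports separate terms, but the simulation classifies intervals without error and the plan does not commit to the split.
- **A day lag can miss the target.** Craving is described as lasting 30–40 minutes. A model using only the previous day ignores the hours before use, so it cannot be the sole test of a precursor. This stands.

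**Conclusion.** The point holds in limited form. As written, the model cannot separate detection of use from a state that precedes use, and a same-window association can therefore be reported as a predictor or high-risk-state marker when it may show only the drug's effect. That conclusion rests on the text: the rationale is pharmacological, and no element of the plan orders heart rate relative to use.

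The size cannot be fixed from the documents, which give no event rates for this sub-study. The simulations agree on direction and should not be quoted as a forecast. Two stronger readings are not supported: that the sub-study is invalid, because detection is a legitimate part of its aim; and that the trial's conclusions are at risk, because this is an optional, preliminary sub-study that does not feed Aims 1 or 2.

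**What to change.** 1. State the unit of analysis and window. Label same-day associations with self-report, and between-test associations with urinalysis, as detection of use.
2. Classify intervals by the plan's own contrast (about 30–40 minutes versus about 2 hours), with a stated rule for lengths in between, and enter short and long intervals as separate terms in place of a pooled count.
3. Add an exploratory lagged model of next-day use, with intervals taken from a preceding day that is use-free on timeline follow-back. If counts are centred within person, keep the outcome day out of the person mean. Do not describe a same-window association alone as a predictor or high-risk-state marker.
4. State that roughly weekly recall and twice-weekly urine, without clock times of use, cannot establish order within a day. A null lagged result then does not rule out a precursor in the hours before use. A use day wrongly recalled as use-free would also carry drug effect into the lagged predictor.

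**Cost.** Wording and one or two extra models. No new collection appears necessary: heart rate is recorded at high resolution, Section 3.2 lists timeline follow-back calendar templates, and the percent-days outcomes in Section 4.1 imply day-level use data. The lagged model will have a wider interval because it keeps fewer use days, about half in the second simulation.
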